4.2.3 Rationale for Endpoints

4.2.3.1 Efficacy Endpoints

The primary endpoint of this study is a biomarker endpoint. There is a need to probe for mechanism given the degree of heterogeneity in humans at the molecular level and then see if there is any relationship between a clinical outcome and putative mechanism. We therefore chose induction of senescence as the primary endpoint. Based on our preliminary data, at least 50% of pts had a >30% change in FLT-PET in their target lesion post DEX. We will therefore use this as our primary endpoint.

Secondary endpoints will include ORR as we are studying the impact of senescence on jump starting response to failed immunotherapy. Response rate in this setting would therefore be an appropriate endpoint as these patients go onto salvage chemotherapy as standard of care with poor response rates of 7 %.

Biomarker Research

Blood samples will be collected and analyzed for T/NK cell counts as well as SASP, including various cytokines and chemokines using a multiplex cytokine array. Phenotypic and functional characterization, including activation markers and intracellular cytokine profile, of immune cell subsets will be evaluated by multi-parametric flow cytometry. The change in FLT-PET will be compared by ORR using an unpaired t-test and the associations with the level of plasma SASP and immune cell activation will be examined by a correlation analysis. Any increase in the absolute number, proliferation or activation of T cells and NK cells in the peripheral blood would indicate a positive response to PD1 therapy (30, 31). The power is not formally justified because these are exploratory and the comparisons are between pre- and post- treatment samples from individual patients.

Multi-factorial immune profiling. Briefly, plasma and PBMC will be isolated from the peripheral blood following standard percoll-gradient centrifugation. A multiplex Luminex assay (R&D Systems) will simultaneously query 45 different cytokines, chemokines, soluble receptors and growth factors (including, IFN- γ , IL-2, IL-2R, IL-6, IL-7, IL-12, IL-15, TNF- α , CCL-2, CCL-4, GRO- α/β , IL-8, IL-10 and VEGF) in the plasma. PBMC will be analyzed via a 12-color flow cytometry to assess:

1. alterations in the absolute number and relative frequency of CD4/CD8 T cells and cytotoxic (CD56^{low}CD16^{high}) and regulatory (CD56^{high}CD16^{low}) NK cells;
2. Proliferation (Ki67) and activation (NKG2D, Perforin, IFN-gamma) markers as well as

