7.2 Treatment Calendar

SCHEDULE OF EVENTS COHORT 1

Procedure	Screening (within 28 days prior to Day 0) ¹	Baseline Day 0	(C1D1)	Lead In C2 and C3	(C2 and 3D1) (± 3Days)	(C4+) (± 3 Days)	EOT	Follow Up ¹
Informed Consent	X							
Medical History	X							
Physical exam	X		X		X	X	X	
Vital Signs	X		X		X	X	X	
ECOG performance status	X		X		X	X	X	
Adverse Events	X		X		X	X	X	X
Concomitant Medications	X		X		X	X	X	X
CBCPD	X		X		X	X	X	
Comp	X		X		X	X	X	
Coagulation (PT/aPTT) ⁷	X							
FDG PET/CT-Chest (VA Ann Arbor) ²	X					X	X	
CT Abdomen/Pelvis ³	X							
Research Blood ⁴		X	X		X			
FLT PET (University of Michigan)		X	X					
Dexamethasone ⁵		X		X	X			
Pembrolizumab ⁶			X		X	X		

¹ Follow Up: Phone call 6 weeks after EOT including any new treatments

² FDG PET/CT-Chest: C4D1 (±7days), then Every 12 weeks (±7days)

³ CT-Abdomen/Pelvis: at screening, C4D1 (±7days), then Every 12 weeks (±7days) **only if disease is present in that area**

⁴ Research Blood: T/TK, SAP, cytokines, chemokines, immune cell subsets; Drawn with 1st FLT PET, 2nd FLT PET, C1D1, C2D1, C3D1 only

⁵ Dexamethasone given orally. Start immediately after FLT PET Day 0 – Day 9. Lead in Day 9-17

⁶ Pembrolizumab given up to 1 year every 21 days

⁷ Only required if clinically indicated or on anticoagulants

SCHEDULE OF EVENTS COHORT 2

Procedure	Screening (within 28 days prior to Day 0) ¹	Baseline Day 0	(C1D1)	Lead In C2 and C3	(C2 and 3D1) (± 3Days)	(C4+) (± 3 Days)	EOT	Follow Up ¹
Informed Consent	X							
Medical History	X							
Physical exam	X		X		X	X	X	
Vital Signs	X		X		X	X	X	
ECOG performance status	X		X		X	X	X	
Adverse Events	X		X		X	X	X	X
Concomitant Medications	X		X		X	X	X	X
CBCPD	X		X		X	X	X	
Comp	X		X		X	X	X	
Coagulation (PT/aPTT) ⁷	X							
FDG PET/CT-Chest (VA Ann Arbor) ²	X					X	X	
CT Abdomen/Pelvis ³	X							
Research Blood ⁴		X	X		X			
FLT PET (University of Michigan)		X	X					
Dexamethasone ⁵		X		X	X			
Pembrolizumab ⁶			X		X	X		

¹ Follow Up: Phone call 6 weeks after EOT including any new treatments

² FDG PET/CT-Chest: C4D1 (±7days), then Every 12 weeks (±7days)

³ CT-Abdomen/Pelvis: at screening, C4D1 (±7days), then Every 12 weeks (±7days) **only if disease is present in that area**

⁴Research Blood: T/TK, SAP, cytokines, chemokines, immune cell subsets; Drawn with 1st FLT PET, 2nd FLT PET, C1D1, C2D1, C3D1 only

⁵ Dexamethasone given orally. Start immediately after FLT PET Day 0 – Day 9. Lead in Day 9-17

⁶Pembrolizumab given up to 1 year every 21 days

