10.5 T and NK cells in PBMC

T cells and NK cells are major contributors to cytolytic function against the tumor, which is often blocked by PD1-PDL1 interaction. Although the number of T cells would deplete to some extent during Dex treatment, it is expected to recover quickly during/following the 3-day washout., while a multi-parametric flow cytometric analysis will detect any change in the number and functions of T and NK cells in the peripheral blood.

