respectively. The secondary endpoints are the changes in SASP and LPFM expression levels between cycle 0 and cycle 1 as well as the expression level of GR at cycle 0. The association between the FLT-PET response and the changes in the expression levels of each of SASP and LPFM will be examined using logistic regression models. The expression levels of SASP and LPFM between cycle 0 and cycle 1 will be examined using a paired t-test, if needed, after data transformation (such as log or square root transformation). The association between the FLT-PET response and the GR expression level will be assessed using logistic regression models. The trajectories from cycle 0 to cycle 4 for the expression levels of each of SASP and LPFM will be examined to see if the expression levels increase monotonically across cycles. To do this, linear mixed-effects models will be used, if needed, after data transformation. In addition, in case that either Cohort B or C becomes the optimal duration, we will descriptively compare the changes in SASP and LPFM expression levels from cycle 0 to cycle 1 between lead-in cohorts. Because these are a discovery study to generate hypotheses, no multiple comparison correction will be made. However, if either the sample size is less than 12 patients or a level (i.e., response vs. non-response) has less than 5 events; all secondary objectives will be exploratory and will be summarized descriptively. All statistical analyses will be based on complete data and no missing data analysis will be performed.

The secondary objective is to assess the effect of DEX on pembrolizumab in terms of overall response rate (ORR), which is the primary endpoint. Based on our previous pre-clinical and clinical studies, we hypothesize that the true ORR of DEX followed by pembrolizumab will be at least 33% (i.e., $p_1 = 0.33$) vs. the historical control whose ORR is at most 7% (i.e., $p_0 = 0.07$). The ORR will be statistically evaluated when the FLT-PET response trial enters the third stage, where the number of patients with the selected optimal DEX duration will be 21. Otherwise, the ORR will be summarized descriptively. The null hypothesis ($p_0 = 7\%$) will be rejected if five or more responses are observed in 21 patients, which yields a 1-sided type I error rate of 5% and power of 87% when the true ORR is 33% (i.e., $p_1 = 33\%$).

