11.3 Population for Analysis

Intent-to-Treat Population: All patients consented and enrolled in the trial.

Evaluable Population: Only those patients who have received at least one cycle of therapy with dexamethasone and pembrolizumab will be considered evaluable.

Safety Evaluable Population: Patients who receive any treatment on protocol will be considered evaluable for safety.

11.4 Analysis of Primary Objective: The primary objective is to identify the smallest duration of fixed dose Dex that results in a >30% reduction in FLTPET. We will utilize a 2 stage design with 3 cohorts (see Statistical schema). The hypothesis is that the true “response” in FLTPET (reduction in FLTPET by >30% following Dex in at least 1 target lesion) will be 60% ($p_1=60$) vs. p_0 30% (based on preliminary data that chemotherapy such as docetaxel results in irreversible cell cycle arrest as measured by S-phase surrogate on FLT-PET (39)).

Secondarily, we will compare FLTPET “response” to GR expression and generation of SASP and immune effector cells. We will also track the trend in immune effector cell response at later time points (cycle 2 and 3) to test contributory effects of pembrolizumab and Dex on the immune phenotype in the blood.

11.5 Analysis of Secondary Objectives The secondary objective is to establish that the true ORR of Dex followed by pembrolizumab will be at least 33% ($p_1 = 0.33$) vs. docetaxel treatment (as the historical control) whose ORR is

$\leq 7\%$ ($p_0 = 0.07$). The ORR will be assessed at a 12 week FDG PET scan. The required sample size for both lead-in FLTPET response and phase 2 studies will range 21 to 31 patients. As secondary objectives, we will explore associations of the change in FLT-PET with ORR assessed by FDG-PET, level of plasma SASP, and immune cell activation. The change in FLT-PET will be compared by ORR using an unpaired t-test and the associations with the level of plasma SASP and immune cell activation will be examined by a correlation analysis. The power is not formally justified because these are exploratory

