14.0 APPENDICES

I. ECOG Performance Status

Grade	Description
0	Normal activity. Fully active, able to carry on all pre-disease performance without restriction.
1	Symptoms, but ambulatory. Restricted in physically strenuous activity, but ambulatory and able to carry out work of a light or sedentary nature (e.g., light housework, office work).
2	In bed <50% of the time. Ambulatory and capable of all self-care, but unable to carry out any work activities. Up and about more than 50% of waking hours.
3	In bed >50% of the time. Capable of only limited self-care, confined to bed or chair more than 50% of waking hours.
4	100% bedridden. Completely disabled. Cannot carry on any self-care. Totally confined to bed or chair.
5	Dead.

* As published in Am. J. Clin. Oncol.: *Oken, M.M., Creech, R.H., Tormey, D.C., Horton, J., Davis, T.E., McFadden, E.T., Carbone, P.P.: Toxicity And Response Criteria Of The Eastern Cooperative Oncology Group. Am J Clin Oncol 5:649-655, 1982.* The Eastern Cooperative Oncology Group, Robert Comis M.D., Group Chair.

II. Common Terminology Criteria for Adverse Events V4.03 (CTCAE)

The descriptions and grading scales found in the revised NCI Common Terminology Criteria for Adverse Events (CTCAE) version 4.0 will be utilized for adverse event reporting. (<https://evs.nci.nih.gov/ftp1/CTCAE/About.html>.)

III Procedure for patients on study

1. Patient will sign consent
2. Patient will have regular standard of care procedures and they will be reviewed and used for eligibility.
3. Patient will be scheduled for baseline FLT PET and FLT PET prior to Pembrolizumab and all future clinic appointments so they know when they will be ahead of time
4. Patient will be called the day before for a reminder of their FLT PET and to start Dexamethasone after FLT PET
5. Patient will go to the University of Michigan for FLT PET and take 1st dose of Dexamethasone immediately afterwards – Coordinator will meet patient for Research blood draw and reimburse patient for this visit (\$25)
6. Patient will be called and reminded to stop taking dexamethasone
7. Patient will be called and reminded about their appointments the next day which are the last FLT PET, visit with [name], cycle 1 of Pembrolizumab infusion
8. Patient will go to the University of Michigan for FLT PET and then come to VA Ann Arbor to begin Pembrolizumab treatment – Patient will be reimbursed to this visit (\$25)

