9. The same thing will happen for the next 2 cycles regarding starting and stopping dexamethasone without the FLT PET
10. Patients will have imaging (FDG-PET and CT-Chest, CT-Abdomen and Pelvis only required if disease is present in that area) at screening, C4D1 (± 7 days), then Every 12 weeks (± 7 days)

IVA. PATIENT'S MEDICATION DIARY COHORT 1 CYCLE 1-3Today's date _____ Agent: **Dexamethasone**

Patient Initials _____ Patient Study ID _____

INSTRUCTIONS TO THE PATIENT:-

- You will take **Dexamethasone orally twice a day, approximately 12 hours apart**
- You should take your capsule(s) at approximately the same time each morning and evening.

Dexamethasone Taper

4mg Dex morning and evenings on Days 10-16; then again on Days 31-37

2mg Dex morning and evenings on Day 17; then again on Day 38

1mg Dex morning and evenings on Day 18; then again on Day 39

Day	Date	Time of Dose		Dexamethasone		Comments	
		AM	PM	_____ mg			
	F	FLT PET @ UM @ _____; Blood Draw; Start Dexamethasone					
		AM	PM	_____mg AM	_____mg PM		
	Sa	AM	PM	_____mg AM	_____mg PM		
	Su	AM	PM	_____mg AM	_____mg PM		
	M	AM	PM	_____mg AM	_____mg PM		
	Tu	AM	PM	_____mg AM	_____mg PM		
	W	AM	PM	_____mg AM	_____mg PM		
	Th	AM	PM	_____mg AM	_____mg PM		
	F	AM	PM	_____mg AM	_____mg PM		
	Sa	AM	PM	_____mg AM	_____mg PM		
	Su	No Dexamethasone					
	M	No Dexamethasone					
	Tu	No Dexamethasone					
1	W	FLT PET @ UM @ _____; Blood Draw; RV w/[name] @ _____; PEMBROLIZUMAB INFUSION (Cycle 1 Day 1 = 1st Dose)					
2	Th						
3	F						
4	Sa						
5	Su						
6	M						
7	Tu						
8	W						
9	Th						
10	F	AM	PM	_____mg AM	_____mg PM		

11	Sa	AM	PM	_____mg AM	_____mg PM
12	Su	AM	PM	_____mg AM	_____mg PM
13	M	AM	PM	_____mg AM	_____mg PM
14	Tu	AM	PM	_____mg AM	_____mg PM
15	W	AM	PM	_____mg AM	_____mg PM
16	Th	AM	PM	_____mg AM	_____mg PM
17	F	AM	PM	_____mg AM	_____mg PM
18	Sa	AM	PM	_____mg AM	_____mg PM
19	Su	No Dexamethasone			
20	M	No Dexamethasone			
21	Tu	No Dexamethasone			
22	W	Blood Draw; RV w/[name] @ _____; PEMBROLIZUMAB INFUSION (Cycle 2 Day 1 = 2nd Dose)			
23	Th				
24	F				
25	Sa				
26	Su				
27	M				
28	Tu				
29	W				
30	Th				
31	F	AM	PM	_____mg AM	_____mg PM
32	Sa	AM	PM	_____mg AM	_____mg PM
33	Su	AM	PM	_____mg AM	_____mg PM
34	M	AM	PM	_____mg AM	_____mg PM
35	Tu	AM	PM	_____mg AM	_____mg PM
36	W	AM	PM	_____mg AM	_____mg PM
37	Th	AM	PM	_____mg AM	_____mg PM
38	F	AM	PM	_____mg AM	_____mg PM
39	Sa	AM	PM	_____mg AM	_____mg PM
40	Su	No Dexamethasone			
41	M	No Dexamethasone			

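### A rise in circulating T or NK cells from Day 0 cannot be credited to pembrolizumab: the first marker interval contains none, every later draw follows another dexamethasone course, and the planned trend pools the two

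*Combined protocol and SAP*

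**What the plan says.** Under Biomarker Research, Section 4.2.3.1 reads the blood markers this way: "Any increase in the absolute number, proliferation or activation of T cells and NK cells in the peripheral blood would indicate a positive response to" (meaning anti-PD-1 treatment). It gives no threshold. It says the comparison is within patient, before against after treatment, but not which draw counts as before.

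Section 11.1 sets the formal contrast: "The secondary endpoints are the changes in SASP and LPFM expression levels between cycle 0 and cycle 1". LPFM is its label for the lymphocyte phenotypic and functional markers. The test is also given: "The expression levels of SASP and LPFM between cycle 0 and cycle 1 will be examined using a paired t-test". The same change enters logistic models against FLT-PET response and against ORR. A mixed model then looks for a monotone increase from cycle 0 to cycle 4.

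Section 11.4 follows the immune cells at cycles 2 and 3 "to test contributory effects of pembrolizumab and Dex on the immune phenotype in the blood".

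The blood schedule in Section 7.2 is "Drawn with 1st FLT PET, 2nd FLT PET, C1D1, C2D1, C3D1 only". Section 10.5 describes what dexamethasone does to the counts: "Although the number of T cells would deplete to some extent during Dex treatment, it is expected to recover quickly during/following the 3-day washout". Section 10.4 expects SASP from dexamethasone-treated tumour to raise the frequency and function of T and NK cells.

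**The concern.** The trial's mechanistic hypothesis has two steps: dexamethasone induces senescence and SASP with immune activation, and the tumour then responds to pembrolizumab. The blood markers are the only repeated measurements of the immune part. Section 4.2.3.1 assigns any rise to PD-1 therapy, yet the protocol itself gives another reason for a rise, namely SASP after dexamethasone. If the draws do not distinguish the two, a published rise from Day 0 could be read as a pharmacodynamic effect of pembrolizumab when the data show only dexamethasone and washout, or the combined regimen. Section 11.4 states the aim of looking at both contributions but names no contrast that would do so.

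**Working it through.** The plan gives no sample size, power or alpha for the marker reading, so there is no stated figure to reproduce. I checked what was given between draws, and then how often the any-increase reading is met by chance.

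**1. Treatment between draws**

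The Day 0 draw comes with the baseline FLT-PET, before the first dexamethasone dose. On C1D1 the diaries list the second FLT-PET, then the blood draw, then "PEMBROLIZUMAB INFUSION (Cycle 1 Day 1 = 1st Dose"). Appendix III agrees that the scan precedes the infusion: "Patient will go to the University of Michigan for FLT PET and then come to VA Ann Arbor to begin Pembrolizumab treatment". The dexamethasone dates below are from the diaries in Appendix IV.

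| Interval | On-trial pembrolizumab doses | Dexamethasone days |
|---|---|---|
| Day 0 to C1D1, all cohorts | 0 | first full course and taper, then 3 days off |
| C1D1 to C2D1, cohort 1 | 1 | days 10–18 = 9 of 21 |
| C1D1 to C2D1, cohort 2 | 1 | days 6–18 = 13 of 21 |
| C1D1 to C2D1, cohort 3 | 1 | days 9–25 = 17 of 28 |
| C2D1 to C3D1 | 1 | same pattern repeated |

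No scheduled draw follows pembrolizumab without a dexamethasone course in between. Footnote 5 of the treatment calendar gives one set of lead-in days (9–17) for all three cohorts, which does not match the diaries and should be reconciled with them. On either set of dates a course precedes the C2D1 draw.

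**2. What the trend from cycle 0 contains**

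Its first step is dexamethasone only. Its later steps are pembrolizumab plus more dexamethasone. A monotone rise is compatible with dexamethasone alone, with pembrolizumab alone after C1D1, or with both.

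**3. How constant is time since dexamethasone?**

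The diaries put 3 dexamethasone-free days before each draw. C2D1 and C3D1 carry a ±3-day window. If the diary dates stay fixed and the visit moves, the gap is 3 − 3 = 0 to 3 + 3 = 6 days; if the minimum washout in Section 4.2.2 is kept, it is 3 to 6. With the half-life of 36–54 h stated there, simple decay over 72 h leaves 2^(−72/36) = 25% to 2^(−72/54) = 40%, so timing may matter.

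**4. Chance of meeting the any-increase reading with no drug effect**

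Assumptions: changes are continuous and symmetric about zero, and there are six readouts (number, proliferation and activation, in T and in NK cells). The count of six is mine; the flow panel lists more. One marker alone rises with probability 0.5. For independent readouts:

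- Any of the six: 1 − 0.5^6 = 0.984
- At least one in each cell type: (1 − 0.5^3)^2 = 0.766
- The same feature in both cell types: 1 − (1 − 0.25)^3 = 0.578

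For equally correlated normal changes, by simulation:

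| Reading | ρ = 0 | ρ = 0.5 | ρ = 0.7 |
|---|---|---|---|
| Any of six | 98% | 86% | 78% |
| At least one in each cell type | 77% | 64% | 60% |
| Same feature in both | 58% | 54% | 53% |

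The range is about 53% to 98%. Even the strictest of these readings is met by chance in more than half of patients.

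**The case against.** The best defence is that no analysis uses the sentence. It stands in the rationale. Section 11 works with levels and changes, never dichotomises a marker as up or not up, and calls the work hypothesis-generating. No stage gate depends on it. The SAP also does not itself attribute the cycle 0 to 1 change to PD-1. It relates that change to FLT-PET response, which is a dexamethasone endpoint, and uses it as a predictor of ORR. For the question of whether dexamethasone activates immune cells, an interval free of pembrolizumab is the right one. All of that stands.

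A reader might go further and infer four things that the documents do not support:

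- **That effects will be misattributed, or patients classified as PD-1 responders.** No such classification is planned. The supportable statement is that the design cannot attribute a rise to pembrolizumab.
- **That steroid rebound will produce false rises over Day 0.** Section 10.5 speaks of recovery. Recovery towards baseline gives no rise over Day 0, and incomplete recovery gives a fall.
- **That there is no reference sample.** A within-patient comparison is stated; what is missing is which draw serves as the reference.
- **That 98% is the false-positive rate.** It is the top of a range and needs six independent readouts with any one sufficing.

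Exploratory status excuses the absence of power. It does not supply the contrast that Section 11.4 needs.

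**Conclusion.** The point holds as a limit on interpretation. A change from Day 0 to C1D1 is a dexamethasone-plus-washout effect. A change from Day 0 to any later draw reflects the combined regimen. The monotone trend from cycle 0 cannot deliver the separation that Section 11.4 seeks. As a reading rule, the any-increase sentence scarcely discriminates.

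This rests on taking cycle 0 as Day 0 and cycle 1 as the C1D1 draw, and on that draw being taken before the infusion, as the diaries list it. Free of pembrolizumab here means on trial only, since every patient has had prior anti-PD-1 or anti-PD-L1 treatment. The primary endpoint, the ORR test and the sample size are unaffected.

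**What to change.** 1. In Section 4.2.3.1, delete the any-increase sentence or restrict it to changes from C1D1.
2. In Sections 11.1 and 11.4, define cycle 0 as Day 0 and cycle 1 as the pre-infusion C1D1 draw. Label the change between them a dexamethasone-plus-washout effect.
3. Add paired C1D1 to C2D1 and C1D1 to C3D1 changes with confidence intervals. Describe them as the change after pembrolizumab plus further dexamethasone, to be read as a pembrolizumab effect only if repeat courses act like the first. State that assumption openly: Section 10.4 expects SASP secretion to persist after washout, which tells against it.
4. Record the actual days from last dexamethasone to each draw, because of the ±3-day window.
5. In the mixed model, code Day 0, C1D1 and the post-pembrolizumab draws as separate levels in place of one trend from cycle 0.
6. Reconcile the cycle 4 time point in Section 11.1 with the blood schedule, which ends at C3D1: either drop it from the model or schedule the draw.

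Items 1 to 5 are wording, recording of dates already in the diaries, and a few more exploratory contrasts on blood already scheduled. Item 6 costs one extra sample per patient if the cycle 4 draw is kept. Neither treatment nor sample size changes. The drugs remain only partly separable, because every contrast after C1D1 on the present schedule still contains dexamethasone.
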